1.3. Study Design

Overview of Study Design and Key Features	
	
informed consent form (ICF) through the final protocol-defined follow-up assessment for survival.
 
 ○ For participants who meet all eligibility criteria and are randomized within the study, the maximum duration of treatment with pembrolizumab, GSK3359609 and placebo is expected to be approximately 2 years, up to 35 cycles. The duration of 5FU-platinum chemotherapy treatment will be 6 cycles (cycle=21 days). ○ The follow-up period begins when study treatment is permanently discontinued; participants will undergo follow-up assessments for safety, PFS on first subsequent anti-cancer therapy (PFS2) and survival as indicated in the Schedule of Activities (SoA) in the protocol.
Study intervention	
 ● 24 mg of GSK3359609 or placebo administered Q3W + 200 mg of pembrolizumab administered Q3W and 5FU-platinum chemotherapy (carboplatin AUC 5 or cisplatin) at 100 mg/m² are each administered as a 30-minute IV infusion once Q3W ● GSK3359609 or placebo will be administered first followed by pembrolizumab; the 6 cycles of 5FU-platinum chemotherapy will be administered after pembrolizumab infusion is complete.
Study intervention Assignment	
 ● Participants will be randomly assigned to either receive the combination of GSK3359609 24 mg + pembrolizumab 200 mg + 5FU-platinum chemotherapy OR placebo + pembrolizumab 200 mg + 5FU-platinum chemotherapy in a 1:1 ratio after stratification
Interim Analysis	
 ● If the study continues to Phase III, there will be two interim analyses for OS, allowing for early stopping of the study due to efficacy or allow for non-binding futility analysis ● For the Phase III study with no enrollment pause, the timing of the two interim analyses will be triggered by the pre-specified number of OS events in the total population. The final analysis of PFS will be aligned with the first OS interim analysis. ● For the Phase II/III study with an enrollment pause, the first interim analyses of OS (IA1, adaptive decision making) will occur when the first 300 participants have a minimum follow-up of 9 months. The timing of the second interim analyses will be triggered by the pre-specified number of OS events in the total population. The final analysis of PFS will be aligned with the second OS interim analysis. ● Results of the interim analyses will be reviewed by an independent data monitoring committee (IDMC). Further details of interim analyses will be provided in the IDMC Charter
Multiplicity	
 ● The family-wise type I error rate is controlled at 2.5% (one-sided) with 0.01% allocated to the PFS hypotheses and 2.49% to the OS hypotheses ● Alpha will be re-allocated as detailed in the multiplicity testing strategy in Section 2.2.

2. STATISTICAL HYPOTHESES/ SUCCESS CRITERIA

2.1. Statistical Hypotheses

The following primary hypotheses will be tested:

Overall Survival (OS)

- Hypotheses (H1): GSK3359609 in combination with pembrolizumab + 5FU/platinum-based chemotherapy prolongs OS compared with placebo in combination with pembrolizumab + 5FU/platinum-based chemotherapy in all participants with R/M HNSCC (total population).
- Hypotheses (H2): GSK3359609 in combination with pembrolizumab + 5FU/platinum-based chemotherapy prolongs OS compared with placebo in combination with pembrolizumab + 5FU/platinum-based chemotherapy in participants with PD-L1 CPS \geq 1 R/M HNSCC.

Progression-free Survival (PFS)

- Hypotheses (H3): GSK3359609 in combination with pembrolizumab + 5FU/platinum-based chemotherapy prolongs PFS per RECIST v1.1 by investigator assessment compared with placebo in combination with pembrolizumab + 5FU/platinum-based chemotherapy in all participants with R/M HNSCC (total population).

The following key secondary hypotheses will be tested:

Progression-free Survival (PFS)

- Hypotheses (H4): GSK3359609 in combination with pembrolizumab + 5FU/platinum-based chemotherapy prolongs PFS per RECIST v1.1 by investigator assessment compared with placebo in combination with pembrolizumab + 5FU/platinum-based chemotherapy in participants with PD-L1 CPS \geq 1 R/M HNSCC.

Time to Deterioration (TTD) in Pain

- Hypothesis (H5): GSK3359609 in combination with pembrolizumab + 5FU/platinum-based chemotherapy prolongs TTD in Pain (measured by EORTC IL51) compared with placebo in combination with pembrolizumab + 5FU/platinum-based chemotherapy in all participants with R/M HNSCC (total population).
- Hypothesis (H6): GSK3359609 in combination with pembrolizumab + 5FU/platinum-based chemotherapy prolongs TTD in Pain (measured by EORTC IL51) compared with placebo in combination with pembrolizumab + 5FU/platinum-based chemotherapy in participants with PD-L1 CPS \geq 1 R/M HNSCC.

TTD in Physical Functioning

- Hypothesis (H7): GSK3359609 in combination with pembrolizumab + 5FU/platinum-based chemotherapy prolongs TTD in Physical Function (measured by PROMIS-PF-8c) compared with placebo in combination with pembrolizumab + 5FU/platinum-based chemotherapy in all participants with R/M HNSCC (total population).
- Hypothesis (H8): GSK3359609 in combination with pembrolizumab + 5FU/platinum-based chemotherapy prolongs TTD in Physical Function (measured by PROMIS-PF-8c) compared with placebo in combination with pembrolizumab + 5FU/platinum-based chemotherapy in participants with PD-L1 CPS \geq 1 R/M HNSCC.

The study is considered to have met the study primary objective if GSK3359609 in combination with pembrolizumab + 5FU/platinum-based chemotherapy is superior to pembrolizumab + 5FU/platinum-based chemotherapy for either OS or PFS in the total population.

[figure not shown]
2.2. Multiple Comparisons and Multiplicity

The primary comparisons of interest are the comparisons between GSK3359609 plus pembrolizumab + 5FU/platinum-based chemotherapy and placebo plus pembrolizumab + 5FU/platinum-based chemotherapy in OS in the total population, OS in the PD-L1 CPS \geq 1 population, and PFS in the total population.

The study employs the graphical method [[Maurer, 2013](#)] to provide strong multiplicity control for multiple hypotheses as well as interim analyses.

The graphical approach is based on closed testing procedures using weighted group sequential Bonferroni tests for the intersection hypotheses. Under the mild monotonicity condition on the error spending functions which is met in this study, it allows the use of sequentially rejective graphical procedures in group sequential trials and controls the family wise error rate in the strong sense. By defining weighted directed graphs, it defines a weighting strategy between and within subfamilies which consist of a subset of null hypotheses each.

Figure 1 Multiplicity Testing Strategy for Comparison Between GSK3359609 in Combination with Pembrolizumab + 5FU/Platinum-based Chemotherapy versus Placebo in Combination with Pembrolizumab + 5FU/Platinum-based Chemotherapy

Abbreviations: C=Chemotherapy; CPS=combined positive score; H = hypothesis; I=GSK3359609; OS=overall survival; P=pembrolizumab; PD-L1= programmed cell death receptor 1-ligand 1; PF=physical function; PFS=progression-free survival; PRO=patient reported outcome; TTD=time to deterioration vs=versus

1. The alpha inside of a box reflects the initial allocated alpha.
2. The alpha level assigned to a family will be rolled over only if the hypotheses within the family are all significant based on the splitting weights for re-allocation presented on the dashed lines connecting families. Within each family, the weights for reallocation from each hypothesis to the others are represented on the solid lines connecting hypotheses.
3. $\epsilon = 49/249$ if H1 and H2 are rejected at the scheduled timing of PFS analysis; $\epsilon = 0$ if H1 and H2 are rejected after the scheduled timing of PFS analysis.

The family-wise type I error for this study is controlled at 2.5% (one-sided). [Figure 1](#) shows the initial one-sided alpha-allocation for OS, PFS, and key PRO endpoints. The multiplicity control strategy applies whether the study remains as a Phase II trial or expands to a Phase III trial.

A one-sided alpha was chosen as, in this placebo-controlled study, pembrolizumab plus chemotherapy is given in both treatment arms. It is not expected that the combination of GSK3359609 and pembrolizumab plus chemotherapy would lead to a detrimental effect due to the active pembrolizumab on both arms and the favourable toxicity profile to date from the addition of GSK3359609 to the SoC. Although the one-sided testing is proposed, as described in Section 9.4.1.1 of the protocol, the 95% two-sided confidence intervals of the treatment effects (hazard ratio for time-to-event endpoints) will be reported, which would provide conclusions on the negative results if there is any statistically significant detrimental effect.

Section 5.2 presents the algorithm and the associated application of the graphical testing strategy illustrated in Figure 1. The R package gMCP [Rohmeyer, 2011] is available to provide functions and graphical user interfaces for graph based multiple test procedures.

Overall Survival

- An initial alpha level of 2.49% is allocated to the OS hypotheses
- If PFS is significant in both the total population and the PD-L1 CPS ≥ 1 population, 0.01% alpha level will be reallocated to the OS hypothesis in the total population and be tested at 2.5% (re-allocated alpha).
- OS for the PD-L1 CPS ≥ 1 population is tested sequentially at the same overall alpha level as that of the OS in the total population if GSK3359609 in combination with pembrolizumab + 5FU/platinum chemotherapy demonstrates superiority to pembrolizumab + 5FU/platinum chemotherapy in OS in the total population. If OS is not significant in the total population, the formal conclusion of statistical significance of OS in the PD-L1 CPS ≥ 1 population will not be drawn.

Refer to Section 3 for alpha- and beta-spending functions used in the OS hypothesis for each possible design.

Efficacy boundaries and non-binding futility boundaries are based on initially assigned type I error rate before any alpha re-allocation and projected number of events at study milestones. The actual boundaries will be determined from the actual number of events at the time of the specified interim analysis using the alpha- and beta- spending functions. Actual futility bounds will be updated if overall beta is changed with respect to alpha roll-over.

Progression-free Survival

- An initial alpha level of 0.01% is allocated to the PFS hypotheses
- If OS is significant in both the total population and PD-L1 CPS ≥ 1 population at the time of the first OS interim analysis, 0.49% alpha level will be re-allocated to PFS hypothesis so that the PFS hypothesis in total population may be tested at 0.5%.
- If the PFS hypothesis in the total population is significant, the hypothesis of PFS in PD-L1 CPS ≥ 1 population will be tested sequentially at the same alpha level.

Key Patient Reported Outcomes (TTD in Pain, TTD in PF)

- Only if GSK3359609 in combination with pembrolizumab +5FU/platinum chemotherapy demonstrates superiority to pembrolizumab + 5FU/platinum in OS in both populations (total population and PD-L1 CPS ≥ 1 population) will key

secondary PRO endpoints be tested. The alpha level from OS hypothesis will be propagated to key PRO hypotheses.

- If OS meets superiority in both the total and PD-L1 CPS \geq 1 populations at the time of the first OS interim analysis, a total of 2.0% alpha level will be propagated to key PRO hypotheses.
- If OS meets superiority in both populations (total population and PD-L1 CPS \geq 1 population) at the time of the second OS interim analysis or the final OS analysis but PFS fails to demonstrate superiority in either population (total population and PD-L1 CPS \geq 1 population), a total of 2.49% alpha level will be propagated to key PRO hypotheses.
- If both OS and PFS demonstrates superiority in both the total population and the PD-L1 CPS \geq 1 population, a total of 2.5% alpha level will be propagated to key PRO hypotheses.
- The alpha level propagated from OS will be equally split between TTD in Pain and TTD in PF, with the possibility to further propagate the alpha level between each other.
- If one of two key PRO hypotheses in the total population is rejected based on the re-allocated alpha level, the key PRO hypotheses in PD-L1 CPS \geq 1 population can be tested based on the (updated) weight, with the possibility to further propagate the levels between each other.
- Based on the re-allocated cumulative alpha level, the nominal significance level for each key PRO endpoint will be calculated based on the Lan-DeMets O’Brien-Fleming approximation alpha-spending function.

3. ANALYSIS SETS

Analysis Set	Definition / Criteria	Analyses Evaluated
Screened	
 • All participants who sign the ICF 	
 • Study population
Enrolled	
 • All participants who entered the study • Participants who were randomized or dosed in error are included in the enrolled population • Note that screening failures (who never passed screening even if rescreened) and participants screened but not needed (Reserve, Not Used) are excluded from the Enrolled analysis set as they did not enter the study. • This population will be based on the study intervention the participant was randomized to 	
 • Study population

Analysis Set	Definition / Criteria	Analyses Evaluated
Modified Intent-To-Treat (mITT)	
 • All randomized participants whether or not randomized intervention was administered, excluding those who were first dosed or randomized after the date of dear investigator letter (DIL) requesting immediate discontinuation of GSK3359609 /placebo. The date of the DIL is the 13th April. • This analysis set will be based on the study intervention to which the participant was randomized and will be the primary analysis set for the analysis of efficacy data • Any participants who receives a study intervention randomization number will be considered to have been randomized 	
 • Study population • Efficacy
Safety	
 • All randomized participants who take at least 1 dose of study intervention • This population will be the primary population for the analyses of safety data. • Participants will be assigned to the actual study intervention group of GSK3359609 plus pembrolizumab + 5FU-platinum chemotherapy if the participant received any dose of GSK3359609 	
 • Safety • Immunogenicity
COVID-19	
 • All participants in the Safety set who had a confirmed, probable or suspected COVID-19 case diagnosis. 	
 • COVID-19 Assessments

3.1. Protocol Deviations

Important protocol deviations (including deviations related to study inclusion/exclusion criteria, conduct of the trial, participant management or participant assessment) will be summarized for the mITT Analysis Set.

Protocol deviations will be tracked by the study team throughout the conduct of the study. These protocol deviations will be reviewed to identify those considered as important as follows:

- Data will be reviewed prior to freezing the database to ensure all important deviations are captured and categorized in the protocol deviations SDTM dataset.
- This dataset will be the basis for the summaries of important protocol deviations.

A separate listing of all inclusion/exclusion criteria deviations will also be provided. This listing will be based on data as recorded on the inclusion/exclusion page of the eCRF.

4. STATISTICAL ANALYSES

4.1. General Considerations

4.1.1. General Methodology

The modified Intent-to-Treat (mITT) analysis set will be used for all study population analyses, efficacy analyses and PRO analyses, unless otherwise specified. The safety analysis set will be used for all safety analyses, unless otherwise specified.

Stratified statistical analyses (the stratified logrank test, the stratified Cox model and the stratified max-combo test) will be based on the following stratification factors, PD-L1 expression (CPS ≥ 20 vs. $1 \leq \text{CPS} < 20$ vs. CPS < 1), and HPV status (positive vs. negative). Participants with oropharynx HPV negative/unknown and non-oropharyngeal tumors will be combined as the HPV negative group in the stratified analyses. The analyses will be performed based on the data collected in Interactive Response Technology (IRT) at randomization will be used, even if it is subsequently discovered that these values were incorrect.

In the case of a substantial amount of wrong stratification assigned at the time of randomization, a sensitivity analysis may be performed based on the data collected in the CRF (or vendor data if collected outside of eCRF).

Confidence intervals will use 95% confidence levels unless otherwise specified.

Unless otherwise specified, continuous data will be summarized using descriptive statistics: n, mean, standard deviation (std), median, minimum and maximum. Categorical data will be summarized as the number and percentage of participants in each category.

Unless otherwise specified, subsequent anticancer therapy will include systemic anticancer therapy, follow-up radiotherapy that is not palliative, or on treatment or follow-up cancer-related surgery/procedures that are not palliative or diagnostic in nature.

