6.5.2. Prohibited Medications and Non-drug Therapies

The following medications are prohibited before the date of randomization (refer to Section 5.2 for specific time requirements) and while on treatment in this study:

- a. Anticancer therapies other than those referred to as Study Intervention/Treatment that include but are not limited to chemotherapy, immunotherapy, biologic therapy, hormonal therapy (other than physiologic replacement), surgery, and radiation therapy (other than palliative intervention as described in Section 6.5.1)
- b. Any investigational drug (s) other than those referred to as Study Intervention/Treatment
- c. Live vaccines such as intra-nasal flu vaccine
- d. Steroids at >10 mg of prednisone per day or equivalent; refer to Section 6.5.1 for permitted use of steroids

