1.2.2. Estimands

Primary and key secondary study objectives are presented in [Table 2](#) with additional information, including prespecified estimands with related attributes.

Due to early study termination, only the primary estimands will be reported in the main CSR.

Table 2 Estimands

Objective (Hypothesis ¹)	Estimand Category	Estimand			
		Variable/ Endpoint ²	Population of interest (Analysis Set)	Intercurrent Event Strategy ³	Population Level Summary Measure

Primary Objective 1:
 
To demonstrate the superiority of GSK3359609 in combination with pembrolizumab + 5FU-platinum chemotherapy compared to pembrolizumab+ 5FU-platinum therapy in OS in the total and PD-L1 CPS ≥ 1 populations in R/M HNSCC (H1, H2)
	Primary	OS	
 Total population (mITT) PD-L1 CPS ≥ 1 population (mITT) 	
 New anti-cancer therapy: treatment policy Treatment discontinuation: treatment policy 	Hazard ratio for GSK3359609+pembrolizumab + 5FU-platinum chemotherapy vs. placebo+pembrolizumab + 5FU-platinum chemotherapy

Primary Objective 2:
 
To demonstrate the superiority of GSK3359609 in combination with pembrolizumab + 5FU-platinum chemotherapy compared to placebo in combination with pembrolizumab + 5FU-platinum chemotherapy in PFS in total population R/M HNSCC (H3)
	Primary	PFS	
 Total population (mITT) 	
 New anti-cancer therapy: hypothetical Treatment discontinuation: treatment policy ≥ 2 missed disease assessments: hypothetical Death: composite 	Hazard ratio for GSK3359609+pembrolizumab + 5FU-platinum chemotherapy vs. placebo+pembrolizumab + 5FU-platinum chemotherapy

[figure not shown]
Objective (Hypothesis ¹)	Estimand Category	Estimand			
		Variable/ Endpoint ²	Population of interest (Analysis Set)	Intercurrent Event Strategy ³	Population Level Summary Measure

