4.2. Primary Endpoint(s) Analysis

4.2.1. Definition of Endpoint(s)

Overall Survival (OS)

Overall Survival (OS) is defined as the interval of time from the date of randomization to the date of death due to any cause.

Participants without documented death will be censored at last known alive date. The last date will be determined by the maximum collection/assessment date from among selected data domains within the clinical database; details will be provided in a separate Output and Programming Specification (OPS) document.

Progression-Free-Survival (PFS) per RECIST v1.1

Progression-free-survival (PFS) per RECIST v1.1 by investigator assessment is defined as the time from the date of randomization to the date of the first objectively documented disease progression per RECIST v1.1 based on investigator assessment, or death due to any cause, whichever occurs first.

The date of disease progression is defined as the date of radiological disease progression based on imaging data per RECIST v1.1. For cases where symptomatic progression is documented by the investigator, the derived response based on tumor assessment data will be utilized.

For participants who receive subsequent anticancer therapy, the following rules will apply:

- If a participant has only a baseline visit or does not have an adequate post-baseline radiological assessment on or prior to the date of initiation of anticancer therapy, PFS will be censored at the date of randomization.
- If anticancer therapy is started without documented disease progression or is started prior to documented disease progression, then PFS will be censored at the date of the last adequate radiological assessment on or prior to the initiation of anticancer therapy (i.e., if an assessment occurs on the same day as the start of new anticancer therapy, the assessment will be used as it is assumed that the assessment occurred prior to the administration of new anticancer therapy). The date of the last adequate radiological assessment will be used as the censoring date.

- If the start date of anticancer therapy is partial, the imputation rules described in the OPS will be applied.

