4.3.2. Supportive Secondary Endpoint(s)

OS rate at 12, 24 and 36 months

The non-parametric Kaplan-Meier method will be used to estimate the survival curves. OS rate at 12 months, 24 months and 36 months, and the corresponding 95% CI will be estimated from the Kaplan-Meier analysis will be reported separately for the total and PD-L1 CPS ≥ 1 populations. The confidence intervals will be based on the Brookmeyer-Crowley method (1982).

If no participants have follow-up duration exceeding the OS milestone, the corresponding summary will not be produced.

A supportive summary of the duration of follow-up will also be produced, presenting the minimum, maximum, median and 25th and 75th percentiles.

Objective Response Rate (ORR) and Disease Control Rate (DCR) per RECIST v1.1

Best Overall Response (BOR)

- The best overall response is the best response recorded from the date of randomization until disease progression or initiation of new anti-cancer therapy, whichever is earlier, as assessed by the investigator per RECIST v1.1. The order from best to worst of the available responses is CR, PR, stable disease (SD), progressive disease (PD) and not evaluable (NE).
- As a randomized double-blind study in which primary endpoints are OS and PFS, the confirmation of CR and PR is not required.
- A subject without any adequate post-baseline assessments will have a BOR of NE.
- To be assigned a status of SD as the best overall response, the minimum criteria for SD duration must be met. Since disease assessment starts at week 9 and a window of ± 7 days is allowed, 56 days since the date of randomization will be used as the minimum criteria for SD duration.

ORR per RECIST v1.1 is defined as the proportion of the participants who have a complete response (CR) or partial response (PR) as the best overall response per RECIST v1.1 based upon investigator assessment.

DCR per RECIST v1.1 is defined as the percentage of participants with a best overall response of CR or PR at any time plus the percentage of participants with SD meeting the minimum time of 15 weeks per RECIST v1.1 based upon investigator assessment. A status of $SD \geq 15$ weeks will be assigned if the follow-up disease assessment has met the SD criteria at least once after the date of randomization at a minimum of 14 weeks (98 days) considering a one-week visit window.

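### SAP 4.1.1 counts non-palliative surgery during treatment as subsequent anticancer therapy but non-palliative radiotherapy only in follow-up, so on-treatment radiotherapy does not censor PFS or DoR

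*SAP*

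**What the plan says.** The only definition of subsequent anticancer therapy in either document is in SAP 4.1.1: "subsequent anticancer therapy will include systemic anticancer therapy, follow-up radiotherapy that is not palliative, or on treatment or follow-up cancer-related surgery/procedures", the surgery and procedures being limited to those that are neither palliative nor diagnostic. It applies unless something else is specified, and no PFS, BOR, DoR or TTD text specifies anything else.

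The PFS rules in SAP 4.2.1 are tied to that term by their opening line: "For participants who receive subsequent anticancer therapy, the following rules will apply". The operative rule is: "If anticancer therapy is started without documented disease progression or is started prior to documented disease progression, then PFS will be censored". The censoring date is that of the last adequate scan on or before the start of the therapy. SAP 4.3.2 takes the DoR censoring rules from the primary PFS analysis.

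The response window in SAP 4.3.2 and the TTD censoring table (SAP Table 4) refer to *new* rather than *subsequent* anticancer therapy. Best overall response is "the best response recorded from the date of randomization until disease progression or initiation of new anti-cancer therapy, whichever is earlier".

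The estimand table in SAP 1.2.2 gives the strategy "New anti-cancer therapy: hypothetical" for PFS and for TTD in pain and physical function. For OS the strategy is treatment policy.

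Protocol 6.5.2 lists, among the anticancer therapies prohibited during treatment, "surgery, and radiation therapy (other than palliative intervention as described in Section 6.5.1". Protocol 6.5.1 allows palliative surgery and palliative radiation on the same terms, case by case with the Medical Monitor.

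**The concern.** The SAP sentence marks both periods for surgery and only one for radiotherapy. The natural reading is that non-palliative radiotherapy given while study treatment continues is not subsequent anticancer therapy. PFS for such a participant would continue past the radiotherapy, and a later progression or death would count as an event. That is how a treatment-policy strategy behaves, not the hypothetical strategy the SAP declares. If the response window follows the same definition, shrinkage after irradiation could also be scored as a response to the study regimen. CR and PR need no confirmation under SAP 4.3.2, so one scan would be enough.

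The planned reporting would not show the effect. SAP 4.2.3 and 4.2.4 drop sensitivity and supplementary analyses for the main CSR, so PFS will not be re-run under another censoring rule.

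**Working it through.** The plan gives no figure on this point, so the check is textual.

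**Step 1. Set the two documents side by side for non-palliative local treatment.**

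| Treatment | Protocol 6.5.2, during treatment | SAP 4.1.1, during treatment | SAP 4.1.1, follow-up |
|---|---|---|---|
| Surgery/procedure | prohibited | counted | counted |
| Radiotherapy | prohibited | not listed | counted |

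The protocol rows are identical and the SAP rows differ in one cell. Palliative treatment is handled alike in both documents: the protocol may permit it for either modality, and the SAP excludes it for either.

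**Step 2. Trace the definition to the endpoints.**

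- PFS: direct. The lead-in to the rules in SAP 4.2.1 uses the defined term.
- DoR: direct, through PFS.
- BOR, ORR, DCR and TTD: indirect. Their rules use *new* anticancer therapy or treatment. The version history records that SAP Version 2 clarified how new anti-cancer therapy is defined, and 4.1.1 is the only place where a definition appears. This supports reading the two as one term but does not say so.
- OS: not reached.

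**Step 3. Follow two hypothetical participants through the rules.** Both have SD at the Week 9 scan, non-palliative local treatment at Week 12 while still on study treatment, PR at Week 15, and PD at the next scan. The Week 12 timing is chosen for illustration. A has surgery, B has radiotherapy. The two terms are read as one.

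- PFS: A is censored at Week 9. B has an event at the later PD.
- BOR: A's window closes at Week 12. Week 9 is 9 × 7 = 63 days, which meets the 56-day minimum, so A's BOR is SD. B's BOR is PR.
- DCR: A's SD at 63 days is short of the 98 days required for durable SD, so A does not count. B counts as a responder.
- DoR: A does not enter. B enters at Week 15 with an event at the later PD.

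The two differ only in the type of local treatment, which the protocol treats alike. If *new* anticancer therapy is instead a separate term whose ordinary meaning includes radiotherapy, B's response window also closes at Week 12, and only the PFS discrepancy remains in this example. DoR would still differ for a participant who responded before the radiotherapy.

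**Step 4. Size.** The effect on the PFS hazard ratio or the ORR difference would need the number of such participants per arm and their outcomes. The documents give neither, so no figure can be computed.

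**The case against.** The strongest objection is that almost nobody will fall into the gap. Inclusion criterion 3 requires disease judged incurable by local therapies. Non-palliative radiotherapy during treatment is prohibited, and protocol deviations are tracked and reviewed before the database is frozen (SAP 3.1). A case needs a protocol breach, before progression, with radiotherapy classed as non-palliative. This stands as an argument about size. It does not explain the asymmetry, because on-treatment surgery is equally prohibited and the SAP counts it.

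The second objection is that the definition need not be exhaustive, since it says what the term will include, and that the Output and Programming Specification (OPS) may fill the gap. The OPS is not among the documents. On anticancer therapy in the PFS rules, SAP 4.2.1 refers to it only for imputing partial start dates. With an explicit on-treatment qualifier for surgery and none for radiotherapy, two programmers could reach different data sets.

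The third objection is that BOR and TTD use a different term. This stands in part, and the reach to those endpoints is conditional for that reason. If the terms do differ, *new* anticancer therapy has no definition, which also needs correcting.

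Two stronger readings are tempting. A reader might infer that ORR or PFS is inflated in favour of the experimental arm. The documents give no frequency, the study is double-blind, and no mechanism for unequal use of radiotherapy is described. Omitting the censoring also adds later events as well as longer follow-up, so the direction is open. A reader might also infer that continued pembrolizumab after feladilimab and placebo were stopped makes such radiotherapy common. No document says so. Amendment 2 moves scans after Week 15 to standard practice, which leaves fewer protocol-scheduled scans at which a response after irradiation could be recorded.

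**Conclusion.** The point holds as a minor defect in a stated rule. As written, non-palliative radiotherapy during study treatment does not censor PFS or DoR, while surgery at the same time would. For PFS this contradicts the declared hypothetical strategy. The extension to BOR, ORR, DCR and TTD rests on reading *new* and *subsequent* anticancer therapy as one term, which the version history supports without stating.

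The number affected is not given and is probably very small. The direction of any between-arm effect is unknown. OS is unaffected because it follows treatment policy. With the study terminated and an abbreviated report planned, a changed conclusion is unlikely. The case for correction is that the derivation should match the estimand and be programmed in only one way.

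**What to change.** In SAP 4.1.1, put *on treatment or* in front of the radiotherapy item so that it covers the same two periods as surgery, and keep the palliative exclusion. Use one term, either *new* or *subsequent*, throughout SAP 4.1.1, 4.2.1, 4.3.1, 4.3.2 and Tables 2 to 4. Apply it to PFS, DoR, BOR/ORR/DCR and TTD. If the difference between radiotherapy and surgery was intended, state the reason.

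The text change is a few words and the derivation gains one condition. A few more participants may be censored. The derivation also needs the date and the palliative or non-palliative intent of on-treatment radiotherapy. The documents do not show that the case report form collects both, so this should be confirmed first. Palliative radiotherapy permitted under Protocol 6.5.1 stays uncounted after the change, as it is now.
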